7.1.1 Change in Infection Status

Uninfected individuals who develop SARS-CoV-2 infection during the study period will be designated as SARS-CoV-2 infected at the time of infection and will be considered to have been enrolled prior to SARS-CoV-2 infection.

7.2 Exclusion Criteria

[figure not shown]
- Individuals who have not yet reached the age of majority
- Unable to provide consent
- Individuals in hospice care
- Any serious medical condition which would prevent long-term participation
- Individuals participating as children in the study NIH RECOVER-Pediatric: Understanding the long-term impact of COVID on children and families; individuals participating as caregivers are eligible for inclusion in the adult protocol
- Incarcerated individuals
- For adult cohort sites only: individuals who were pregnant at the time of their COVID infection or qualifying negative test, and whose pregnancy is ongoing.
- For adult cohort sites only: individuals who were pregnant at the time of their COVID infection or qualifying negative test, and whose pregnancy is completed and resulted in a live birth.
 - Individuals who were pregnant at the time of COVID or qualifying negative test and who did not have a live birth remain eligible for inclusion at adult cohort sites.
 - Individuals who were pregnant at the time of COVID or are currently pregnant, regardless of pregnancy outcome, remain eligible for inclusion at pregnancy cohort sites
- For pregnancy cohort sites only: pregnant participants with an estimated date of delivery on or after December 31, 2023.

Note that participation in other observational or intervention studies while participating in RECOVER is not an exclusion criterion.

7.3 Vulnerable Populations

7.3.1 Pregnant Participants

Data from pregnant participants will be included as part of the study as it is important to understand COVID-19 in all populations. The study cannot be conducted without the group because pregnant participants represent a portion of the population affected by COVID-19 and their responses to COVID-19

disease may be different from that of the general population. No inducements, monetary or otherwise, will be offered to terminate a pregnancy. Individuals engaged in the research will have no part in any decisions as to the timing, method or procedures used to terminate a pregnancy. Individuals engaged in the research will have no part in determining the viability of a neonate. Participants who were pregnant while they had COVID-19 will be offered the opportunity to enroll their infants (once born) in the NIH RECOVER-Pediatric: Understanding the long-term impact of COVID on children and families study if they are being enrolled at a site that also supports the pediatric study. Agreement to participate in the pediatric protocol is not required for participation in the adult protocol. Similarly, agreement to participate in the pediatric protocol does not require participation in the adult protocol. This option will only be available to the participants at the pregnancy sites in the RECOVER Network and is consistent with the pediatric protocol. At these sites, participants who had Covid while pregnant and gave birth before enrollment in RECOVER, will have their medical information during pregnancy collected and used in this protocol.

7.3.2 Prisoners

Long-term incarcerated individuals will not be enrolled in the study. If an enrolled participant becomes incarcerated, the IRB should be notified immediately. If the incarceration is short-term (i.e., less than 90 days), the participant can remain in the study.

7.3.3 Students and Employees

Students and employees recruited as research subjects are more vulnerable to coercion or undue influence. Students may feel their participation in research is necessary as part of their academic requirements, or that failing to participate will negatively impact their relationship and academic/professional opportunities with the instructor/investigator. Employees may feel unable to exercise free choice in their decision to participate, due to belief that their decision may affect (favorably or unfavorably) their performance evaluations, advancement opportunities, or other employment-related decisions. The appearance of coercion and undue influence of employees/students must be minimized in recruitment methods, including the informed consent process, and other procedures. The informed consent process must include a discussion stating that the subject's decision to participate will not impact the status of employment, academic status, and/or grades respective to the target subject population.

Students or employees will not be specifically targeted for participation in this protocol but will also not be excluded based on these protected statuses. Passive recruitment methods, such as those that require the employee/student to reach out regarding participation include, but are not limited to: an unassociated, non-supervisory recruiter; IRB-approved flyers; site-wide e-mails to specific groups that encourage those interested to reach out for information. All prospectively enrolled students or employees will be informed of the specific risks to privacy and confidentiality that may be compromised prior to signing consent. This information may include sensitive topics included in the RECOVER protocol including, but not limited to, comorbidities, mental health, sexual behavior, and/or drug/alcohol use.

7.4 Loss to Follow-up

Subjects may be considered lost to follow-up if they have missed at least three consecutive study visits and are not responsive to the site's contact attempts or offers to reduce participant burden (see **Retention Strategy**). For each missed visit, the site should attempt to contact the participant through at least three different methods at different times. Contact methods include, but are not limited to, email, phone calls, certified letters, and/or contacting their emergency contact. An IRB-approved appointment reminder letter can be used for this purpose. If a participant contacts or returns to the site even after multiple missed follow-up visits, they should be given the option to resume participation in the study. If a participant is lost to follow-up or declines future visits, their data will be retained for future use unless they provide written documentation to withdraw their consent (see Section 7.5); however, no additional data will be collected.

Should a study participant return after a period of no contact, study staff should conduct the closest visit based on their schedule.

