4.1 Known Potential Risks

This study includes patient-reported questionnaires, data extraction from electronic health records (EHR) and claims data, basic clinical examinations, blood draws, and radiology studies. We describe the risks of each in turn. Some patients (maximum of 20%) will be asked to undergo moderate risk procedures; these patients will be separately consented for those procedures. Clinical consent will be signed as per each local institution's requirements and policies for procedures that require clinical consent. These clinical consents will be administered in addition to the complete research consents, with all of the risks outlined, administered by the research team, for tests such as colonoscopy, endoscopy, flexible bronchoscopy, and right heart catheterization.

Risks of survey completion: While we anticipate no risk greater than that found in everyday life from survey completion, we understand that completing questionnaires about the COVID-19 experience could cause subjects to become upset or frustrated. To minimize risk, staff will be trained to let subjects know that they can stop the line of questioning at any point and ask for the subject to notify them if and/or when they are ready to resume the questioning.

Additionally, loss of confidentiality for the subjects' answers is another potential risk. Loss of confidentiality could result in damage to a patient's financial standing, employability, insurability, or reputation. The aforementioned risk is significantly minimized through the use of a secure, encrypted, password-protected database such as i2b2 Data Hub REDCap Central residing in a protected cloud environment. Minimal necessary access to the REDCap database will be granted only to study and research personnel. The REDCap Central database and the i2b2 Data Hub will meet compliance with FISMA-Moderate federal standards.

[figure not shown]
PHI that may link subjects to the data will be stored in REDCap Central. In the databases used for analyses, such as the i2b2 Data Hub, there will be a HIPAA-defined coded Limited Data Set. Universally Unique Identifiers (UUIDs) will be generated from PHI to maintain unique, non-duplicated subject identifiers across the analysis databases used in the study (see section 13.4.2).

Any PHI that may link subjects to the data will be stored in a separate location.

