A preexisting condition is one that is present at the start of the study. A preexisting condition should be recorded as an adverse event if the frequency, intensity, or the character of the condition worsens during the study period and is not captured in existing RECOVER study forms as detailed above.

Post-study Adverse Event

At the last scheduled visit, the investigator should instruct each subject to report any subsequent event(s) that the subject, or the subject's personal physician, believes might reasonably be related to participation in this study. The investigator should notify the study sponsor of any death or adverse event occurring at any time after a subject has discontinued or terminated study participation that may reasonably be related to this study.

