13.3 Informed Consent Process

When the enrollment visit is completed in person, informed consent will be obtained and documented in writing before participation in study procedures. When the enrollment visit is completed remotely, electronic

consent will be used. Study sites will identify potential subjects in their available recruitment pools (extant cohorts, clinical cohorts, acute cohorts, and/or post-acute cohorts). Once potential subjects are identified through standard processes by the study team, the research study will be explained in lay terms to each potential research subject in their preferred language, either one-on-one or in a group session. If through a group information session, no patient identifiers will be collected during the session. In addition, if using a group session, potential subjects must have an opportunity to meet individually with study staff after the group session to ask questions and provide written consent in a private setting. The option to use group information sessions will help with (1) meeting recruitment goals in a timely manner; (2) overcoming the challenges of patients not showing up for screening appointments; and (3) scheduling more than one subject visit per time slot.

The overall common consent document(s) will include:

- 1) consent for participation in all minimal risk RECOVER Tier 1, 2 and 3 activities;
- 2) consent for sharing identifiable data with the secure REDCap Central database;
- 3) consent to obtain and link data from electronic health records, regional health information exchanges, claims data and the National Death Index:
- 4) consent for sharing of deidentified data and specimens through RECOVER databases and specimen repositories (in addition to other NIH-designated repositories).
- 5) optional collection of biospecimens
- 6) If biospecimens are collected, additional optional collection of genetic sample for testing and optional consent for return of genetic information

[figure not shown]
Separate consent will be obtained by the pediatric study team from a person who was pregnant while infected with COVID-19 for the infant to participate in the pediatric study, if applicable.

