13.4 Subject and Data Confidentiality

Information about study subjects will be kept confidential and managed according to the requirements of the Health Insurance Portability and Accountability Act of 1996 (HIPAA). Those regulations require a signed subject authorization informing the subject of the following:

- What protected health information (PHI) will be collected from subjects in this study
- Who will have access to that information and why
- Who will use or disclose that information
- The rights of a research subject to revoke their authorization for use of their PHI.

In the event that a subject revokes authorization to collect or use PHI, the investigator, by regulation, retains the ability to use all information collected prior to the revocation of subject authorization. For subjects that have revoked authorization to collect or use PHI, attempts should be made to obtain permission to collect at least vital status (i.e. that the subject is alive) at the end of their scheduled study period.

Investigators in this research will take all reasonable measures to protect the confidentiality of the medical records of patients and their families. Measures to protect confidentiality are as follows:

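### Section 7.4 ends all data collection at loss to follow-up, with no exemption for the record and death-index linkage that the common consent covers

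*Protocol*

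**What the plan says.** Section 7.4 of the protocol allows a participant to be classed as lost after having "missed at least three consecutive study visits" and failing to respond to the site. The rule on data then follows: "If a participant is lost to follow-up or declines future visits, their data will be retained for future use", and the sentence goes on "unless they provide written documentation to withdraw their consent (see Section 7.5); however, no additional data will be collected". Written withdrawal under section 7.5 is thus the only exception to retention, and the closing clause does not confine the stop to visits, surveys or specimens. Someone who later returns may resume.

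Section 13.3 lists what the common consent contains. Item 3 is "consent to obtain and link data from electronic health records, regional health information exchanges, claims data and the National Death Index". Items 5 and 6 are marked optional; item 3 is not. Section 4.1 counts "data extraction from electronic health records (EHR) and claims data" among the study's activities, and section 12.6.2.1 names EHR repository data as a data type.

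The Protocol Summary gives incident clinical disease and organ injury as secondary endpoints, with follow-up of up to four years.

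**The concern.** Passive sources are most useful once a participant can no longer be reached, because they need no visit and no reply. Section 7.4 as worded switches them off at that moment, for people who have revoked nothing. Section 7.5 puts the same stop on new data for people who do withdraw consent, so for later follow-up non-attendance is treated like withdrawal.

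At stake is the completeness of diagnosed disease after contact is lost, and knowledge of deaths, which act as competing or censoring events in any incidence estimate. A participant who becomes gravely ill may miss visits and stop replying, so loss may depend on the outcome, and it may do so differently in infected and uninfected participants. An analysis plan cannot recover data that the protocol says not to collect.

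**Working it through.** The protocol has no figure to reproduce on this point, so the check is mainly a comparison of sections.

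1. **Who is affected.** Section 7.4 covers the unreachable and those who decline visits, short of written withdrawal. At the 90-day interval of section 8.3, three missed visits span 3 × 90 = 270 days, about nine months.
2. **What stops.** The clause names no type of data, and no other section says that linkage continues after loss to follow-up.
3. **What was agreed to.** Section 13.3 item 3 covers EHR, health information exchange, claims and National Death Index data.
4. **Rules nearby.** Section 13.4 says that for people who revoke authorization "attempts should be made to obtain permission to collect at least vital status"; section 7.4 has no vital-status step for people who revoked nothing. Section 10.1 says "The investigator should notify the study sponsor of any death or adverse event occurring at any time after a subject has discontinued" or terminated participation, but only where the event may reasonably be related to the study. Section 10.2 follows events until they resolve, stabilise or are found not to be caused by participation. These are contrasts and safety duties; none provides general follow-up for disease or death.
5. **Which endpoints linkage could serve.** Appendix 1 has participants complete the PASC symptom form themselves, so linkage cannot replace it. Diagnosed incident disease can appear in EHR and claims records, and deaths in the death index.

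**Scale, on assumed values only.** The protocol gives neither attrition nor an incident-disease rate. Let *d* be the proportion lost, *p* = 10% the risk in those who stay, *r* the ratio of risk in the lost to risk in those who stay, and suppose half of the lost participants' events fall after contact ends.

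- Overall risk = (1 − *d*)*p* + *d·r·p*
- Share of all events unrecorded = 0.5·*d·r·p* / overall risk

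| *d* | *r* | Overall risk | Share unrecorded |
|---|---|---|---|
| 10% | 1.0 | 10.0% | 0.5/10.0 = 5.0% |
| 20% | 1.5 | 0.8×10 + 0.2×15 = 11.0% | 1.5/11.0 = 13.6% |
| 30% | 2.0 | 0.7×10 + 0.3×20 = 13.0% | 3.0/13.0 = 23.1% |

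The share is of events missed, on the premise that no one returns and that linkage would find every event. It is not a bias. With *r* = 1, censoring is uninformative and the loss is mainly of precision. With *r* above 1, a risk taken from those who stay is too low; with *r* below 1 it is too high.

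**The case against.** The strongest reply is that section 7.4 concerns missed visits and contact attempts and never mentions linkage, so the clause may mean only that site collection ends. The same sentence keeps data for future use, and section 9.9.1 describes tokens that may allow later linkage to national datasets. That intention is possible, but the text does not state it, and sites and the data core work from the text.

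Several stronger inferences are tempting, and here the reply succeeds:

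- A reader might infer that deaths will be coded as loss to follow-up. The protocol does not say so. Each missed visit calls for at least three contact methods, the emergency contact is among those listed, and alternate contacts are refreshed every three months (Appendix 2). Some deaths will surface this way.
- A reader might infer a direct contradiction with sections 10.1, 10.2 and 13.4. Section 13.4 is about asking permission, which an unreachable person cannot give, and sections 10.1 and 10.2 are safety duties. They can coexist with section 7.4, though the wording should be reconciled.
- A reader might infer that hypotheses 1b, 1c and 2b lose the data they need. To the extent that these rest on symptom-defined sequelae and recovery, linkage cannot supply the outcome. It offers deaths and some information about who drops out.
- A reader might infer a bias of known size. All rates would be assumed, its direction depends on who leaves (healthy controls losing interest would reverse the sign in that group), and data from before dropout are retained.

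The reply also has force for people who actively decline visits. Section 7.4 lets them stop without the data removal and specimen destruction of section 7.5. Continuing to draw their records by default is a consent trade-off, and stopping is a defensible choice.

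**Conclusion.** The point holds in limited form. As written, section 7.4 discards consented passive follow-up for participants who are lost but have not withdrawn, and no other section exempts it. The consequence falls on incident diagnosed disease and on some deaths after loss of contact, among those who never return. Death is not itself a listed endpoint; it matters as a competing or censoring event.

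The size of any bias cannot be derived from the protocol. The 5% to 23% of events in the table shows scale under stated assumptions and is not an estimate for this study. The primary endpoint, candidate PASC symptoms, would not be rescued by linkage.

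The conclusion rests on the literal reading of section 7.4 and on section 13.3's description of the consent; the consent form itself was not available. This is an inexpensive improvement worth making, not a threat to the study's main results.

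**What to change.** Amend section 7.4 along these lines:

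> For participants lost to follow-up, active contact, visits, surveys and specimen collection stop. Linkage to electronic health records, health information exchanges, claims and the National Death Index, as consented, continues to study end unless consent or authorization is withdrawn. Participants who decline further visits are asked about linkage, and it continues only if they do not object.

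The option for returning participants to resume should stay. Record the date of last active contact separately from the date passive follow-up ends, so that symptom outcomes and linked outcomes can be censored at their own dates. Reconcile the wording with sections 7.5, 10.1, 10.2, 13.3 and 13.4.

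The cost is an IRB amendment, a check that the consent wording covers people who have stopped attending, and modest linkage work. Section 9.9.1 only says that sites may generate linkage tokens, so how far linkage is already in place also needs confirming.

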7.5 Subject Withdrawal

Subjects are free to stop participating in the study at any time upon request. However, if the subject desires to withdraw consent from participation, this includes removal of collected data from prospective analyses and destruction of any unused biospecimens. The subject must provide a written notice of withdrawal of their consent (either via letter or e-mail) to the study site PI clearly stating that they wish all eligible data removed from prospective analyses and unused biospecimens (if collected) to be destroyed. Once the subjects withdraw their consent to participate, no more information will be collected. However, in cases when the data removal will affect the integrity of the study, all previously collected data will not be removed. Subjects will be informed about this during the consenting process. Data that have already been distributed to the i2b2 Data Hub will not be removed. Subjects may not re-enroll in the study once they have withdrawn their consent, and removal of data from prospective analyses cannot be reversed, nor destroyed biospecimens restored.

7.6 Premature Termination or Suspension of the Study or a Participant

This study or a participant may be temporarily suspended or prematurely terminated if there is sufficient reasonable cause. Written notification, documenting the reason for suspension or termination, will be provided by the suspending or terminating party to the NIH Sponsor and site investigators. If the study is prematurely terminated or suspended, the site PI will promptly inform the IRB and will provide the reason(s) for the termination or suspension.

Circumstances that may warrant termination or suspension include, but are not limited to:

- Determination of unexpected, significant, or unacceptable risk to participants
- Insufficient compliance to protocol requirements
- Data that are not sufficiently complete and/or evaluable
- Determination of futility

Study may resume once concerns about safety, protocol compliance, and data quality are addressed and satisfy the sponsor and/or IRB.

8 Study Schedule

8.1 Overview of Study Schedule

Data will be collected at baseline and then following the study schedule, which starts at time of first infection for those enrolled during first infection or after their first infection without an active infection at time of enrollment; at time of reinfection if enrolled during an acute infection; or at time of negative COVID-19 test, for those who are uninfected. Uninfected pregnant individuals will begin the study schedule on their delivery date. See **Table 3**. Collection will be tiered such that all enrolled patients will undergo Tier 1 data collection, and those with abnormal findings on Tier 1 collection may progress to more intensive, invasive, or costly Tier 2 and Tier 3 data collection. We anticipate that approximately 30% of participants will undergo each Tier 2 test and a maximum of 20% of enrollees will undergo each Tier 3 test for any given symptom, including both those with relevant symptoms and a random sample of 5.6% of SARS-CoV-2 infected and 11.4% of uninfected subjects without relevant symptoms. All patients will undergo at least one in-person visit annually, which can be provided at home if provisions are made for home blood and biospecimen collection.

Table 3: Index date and study schedule date, by enrollment type

Enrollment Category	Index Date	Study Schedule Start Date	
Acute Infected (First Infection)	First positive SARS-CoV-2 test	First positive SARS-CoV-2 test	
	result date or, if test not	result date or, if test not	

	available, date of COVID symptom onset	available, date of COVID symptom onset
Acute Infected (Reinfected)	First positive SARS-CoV-2 test result date or, if test not available, date of COVID symptom onset	Most recent positive SARS- CoV-2 test result date or, if test not available, date of COVID symptom onset
Acute Uninfected	Qualifying negative SARS-CoV-2 test result date	Qualifying negative SARS-CoV-2 test result date
Post-Acute Infected	First positive SARS-CoV-2 test result date or, if test not available, date of COVID symptom onset	First positive SARS-CoV-2 test result date or, if test not available, date of COVID symptom onset
Post-Acute Uninfected	Qualifying negative SARS-CoV-2 test result date. For pregnancy sites only , index date is the prior delivery date	Qualifying negative SARS-CoV-2 test result date. For pregnancy sites only , index date is the prior delivery date

Home Visits

Some study testing or procedures may be conducted through home visits to alleviate travel burden for subjects. These home study visits will be conducted by members of the clinical research study staff or contracted clinical examiners (such as Exam One) and will follow COVID safety protocols for the duration of the visit. As only delegated staff will be performing these visits, responses and specimens collected will be strictly confidential. These study visits will be strictly for data and/or specimen collection and all research tests and procedures which may be performed through home visits are indicated in **Appendix 3**: Tier 2 questions, tests and procedures and **Appendix 4**: Tier 3 tests and procedures.

